### **3.6 Study Drug Administration**

G03-52-01 will be administered IM as a single dose at concentrations of 10 mg, 25 mg, 50 mg, and 100 mg by varying the administration volume. Placebo will be 0.9% Sodium Chloride Injection, USP is a sterile, non-pyrogenic, isotonic solution of sodium chloride and water for injection.

G03-52-01 and placebo should be administered as a single IM injection to the central, thickest portion of the deltoid and the injection must be completed within 30 minutes after preparation.

### **3.7 Concomitant Medications**

Concomitant medication information will be recorded at Screening for the prior 28 days. At each subsequent study visit each new concomitant medication and changes to existing medications will be recorded. Subjects will be required not to utilize non-study medication or herbal supplements during the study except those deemed necessary by the site PI or sub investigator. Any drug (e.g., over-the-counter herbal supplement, vitamins or prescription) use by the subject during the course of the trial will be recorded in the subject's source documents and on the appropriate eCRF.

Subjects will be instructed to refrain from the receipt of any of the medication/ product as per Section 5.8 of the protocol during study participation unless medically indicated and deemed immediately necessary by their private physician.

### **3.8 Drug Administration and Compliance**

G03-52-01 and placebo should be administered as a single IM injection to the central, thickest portion of the deltoid. Water for injection will be used to reconstitute the G03-52-01 for IM injection. The placebo will be normal saline without the addition of G03-52-01. The product should be used within 30 minutes upon reconstitution.

Complete records and documentation of study product receipt, accountability, dispensation, temperature monitoring, and storage conditions, and final disposition of the study product will be maintained. All study products, whether administered or not, must be documented on the appropriate study product accountability record or dispensing log.

### **3.9 Evaluation of Efficacy**

Not Applicable

### **3.10 Evaluation Pharmacokinetic and Sampling Schedule**

Six-mL samples of blood for PK samples will be drawn at the following times: pre-dose, and at 2, 4, 8, 24, 48, and 72 hours post dose and on Days 4, 8, 15, 30, 45, 60, 90, and 120 for cohorts 1-3 & pre-dose, at 6 hours post-dose, and on days 1, 2, 4, 8, 15, 30, 45, 60, 90, 120 and 180 for cohort 4. Serum will be analyzed for levels of each of the monoclonal antibodies using a validated ECLA or ELISA. All PK samples will be tested by ECLA or ELISA.

Three 10-mL samples of blood will be drawn to be analyzed for neutralizing antibody concentrated using the validated Battelle MNA. PK samples will be tested by the Battelle MNA for serotypes A and B at pre-dose and on Days 4, 30, 60, 90, and 120 for cohorts 1-3 & at pre-dose, and on days 4, 30, 45, 60, 90 and 120 for cohort 4.

PK samples will be collected as described in [Table 3-2](#).

### **3.11 Evaluation of Pharmacodynamics and Sampling Schedule**

Not Applicable

### **3.12 Evaluation of Immunogenicity and Sampling Schedule**

Six-mL samples of blood will be drawn at pre-dose, on Days 15, 30, 45, 60, 90, and 120 for determining the presence of ADA using a validated ECLA that measures of total anti-drug antibody in serum for Cohorts 1-3.

Six-mL samples of blood will be drawn pre-dose and on Days 45, 60, 90, 120, and 180 for determining the presence of ADA using a validated ECLA that measures total anti-drug antibody in serum for Cohort 4. This will be done to assess immunogenicity.

Immunogenicity samples will be collected as described in [Table 3-2](#).

### **3.13 Evaluation of Other Parameters and Sampling Schedule**

Not Applicable

### **3.14 Evaluation of Treatment Safety**

Study products safety will be assessed as per sections 3.15 to 3.21.

### **3.15 Adverse Events**

An AE is defined as any untoward medical occurrence in a subject administered a pharmaceutical product during the course of a clinical investigation. An AE can therefore be any

unfavorable and unintended sign, symptom, or disease temporally associated with the use of a study drug, whether or not thought to be related to the study drug.

A treatment-emergent AE (TEAE) is defined as any event not present before exposure to study drug or any event already present that worsens in either intensity or frequency after exposure to study drug.

An SAE is any untoward medical occurrence that at any dose:

- Results in death,
- Is life-threatening\*,
- Requires inpatient hospitalization or prolongation of existing hospitalization,
- Congenital anomaly/birth defect;
- Persistent or significant incapacity or substantial disruption of the ability to conduct normal life functions

*\*Life-threatening adverse event. An adverse event is considered “life-threatening” if, in the view of either the investigator or sponsor, its occurrence places the patient or subject at immediate risk of death. It does not include an adverse event, had it occurred in a more severe form, might have caused death.*

Subjects will be monitored throughout the study for AEs, from the time informed consent is obtained through End of Study (EOS). Any medical condition that is present at the time the subject is screened should be considered as baseline and not reported as an AE. However, if the condition increases in severity or frequency at any time during the study, it should be recorded as an AE.

All AEs must be graded for severity and relationship to study product based on the Investigator's assessment. AEs will be followed until resolution or stability even if this extends beyond the study-reporting period. Resolution of an AE is defined as the return to pretreatment status or stabilization of the condition with the expectation that it will remain chronic. Follow-up procedures, evaluations, and outcomes will be recorded on the subject's case report forms.

The following details will be collected: description of the AE, onset date, action taken with study drug (dose not changed, dose reduced, drug interruption, drug withdrawn, dose increased and not applicable), date of resolution, outcome (recovered/resolved, not recovered/not resolved, recovered/resolved with sequelae, recovering/resolving, fatal and unknown), severity (mild, moderate, severe), seriousness (yes, no), causality/relationship to study drug (not related, possibly related and definitely related), additional treatment required.

Reactogenicity (Other conditions, local and systemic reactions) will also be collected.

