4. STUDY DESIGN

This is a Phase 1, single-center, placebo-controlled, double-blind, dose-escalation study to evaluate the safety and tolerability of G03-52-01 in healthy adults. This is a first-in-human study consisting of four Cohorts of ten subjects each. Each subject will receive a single IM injection of G03-52-01 or placebo.

Table 1: Cohorts

Cohort	Dose of G03-52-01	Number of Subjects
1	10 mg	10 subjects (8 active, 2 placebo)
2	25 mg	10 subjects (8 active, 2 placebo)
3	50 mg	10 subjects (8 active, 2 placebo)
4	100 mg	10 subjects (8 active, 2 placebo)

Schedule for Subjects

Subjects in Cohorts 1-3 will participate in the study for approximately 150 days, including a 28-day screening period, up to 12-hour inpatient stay and approximately 120-day follow-up after study product administration. Subjects will remain at the clinic and not be eligible for discharge until 8 hours after the IM injection. Last follow up visit scheduled at Day 120.

Subjects in Cohort 4 will participate in the study for approximately 210 days, including a 28-day screening period, up to a 12-hour clinic stay and approximately 180-day follow-up after study product administration. Subjects will remain at the clinic and not be eligible for discharge until approximately 8 hours after the IM injection. Last follow up visit scheduled at Day 180.

The end of the study is defined as the date of the last visit of the last subject in the study.

Schedule for Cohorts

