Diarrhea	2-3 loose or watery stools or <400 g/24 hours	4-5 loose or watery stools or 400-800 g/24 hours	≥6 loose or watery stools or >800g/24 hours OR requires IV hydration OR requires medical intervention
REACTOGENICITY			
LOCAL REACTIONS	Mild (Grade 1)	Moderate (Grade 2)	Severe (Grade 3)
Pain – experienced without touching the injection site (spontaneous discomfort)	Does not interfere with activity	Repeated use of non-narcotic pain reliever >24 hours OR interferes with activity	Any use of narcotic pain reliever OR prevents daily activity
Tenderness – hurts only when injection site is touched, or the arm is moved	Discomfort only to touch	Discomfort with movement	Significant discomfort at rest
Pruritus (Itching)	Does not interfere with daily activity	Interferes with daily activity	Prevents daily activity
Ecchymosis (Bruising)*	Does not interfere with daily activity	Interferes with daily activity	Prevents daily activity
Erythema (Redness)*	Does not interfere with daily activity	Interferes with daily activity	Prevents daily activity
Induration (Hardness)/Swelling*	Does not interfere with daily activity	Interferes with daily activity	Prevents daily activity
Nodule	Does not interfere with daily activity	Interferes with daily activity	Prevents daily activity
Ulcer	Does not interfere with daily activity	Interferes with daily activity	Prevents daily activity
Ecchymosis (Bruising)*	25 mm – 50 mm	51 mm – 100 mm	>100 mm
Erythema (Redness)*	25 mm – 50 mm	51 mm – 100 mm	>100 mm
Induration (Hardness)/Swelling*	25 mm – 50 mm	51 mm – 100 mm	>100 mm
Nodule	25 mm – 50 mm	51 mm – 100 mm	>100 mm
Ulcer	1 mm – 50 mm	51 mm – 100 mm	>100 mm
SYSTEMIC REACTIONS	Mild (Grade 1)	Moderate (Grade 2)	Severe (Grade 3)
Allergic Reaction	Pruritus without rash	Localized urticaria OR requires oral therapy	Generalized urticaria; angioedema OR

			anaphylaxis OR requires epinephrine
Headache	No interference with activity	Repeated use of non-narcotic pain reliever >24 hours OR some interference with activity	Significant; any use of narcotic pain reliever OR prevents daily activity OR requires triptans
Fatigue	No interference with activity	Some interference with activity	Significant; prevents daily activity
Myalgia	No interference with activity	Some interference with activity	Significant; prevents daily activity
All Other conditions	Mild (Grade 1)	Moderate (Grade 2)	Severe (Grade 3)

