Illness or clinical AE (as defined according to applicable regulations)	No interference with activity	Some interference with activity not requiring medical intervention	Prevents daily activity and requires medical intervention

*Will not be used as halting criteria

Laboratory and Vital Signs Reference Ranges, Eligibility Ranges, and Toxicity Grading

Laboratory Adverse Events*	Mild	Moderate	Severe	ICON Normal Lab Values
	(Grade 1)	(Grade 2)	(Grade 3)	
Blood, Serum, or Plasma				
Sodium (hyponatremia) – mEq/L	131-132	129-130	<129	133 – 143
Sodium (hypernatremia) – mEq/L	144 – 145	146 – 147	>147	133 – 143
Potassium (hyperkalemia) – mEq/L	5.2 – 5.4	5.5 – 5.6	>5.6	3.5 - 5.1
Potassium (hypokalemia) – mEq/L	3.2-3.4	3.0 – 3.1	<3.0	3.5 - 5.1
Glucose (hypoglycemia) – mg/dL	65 – 69	55 – 64	<55	70 – 105
Glucose (hyperglycemia) – mg/dL Fasting	106 – 125	126 – 200	>200	70 – 105
Blood Urea Nitrogen – mg/dL	21-26	27 – 31	> 31	6 – 20
Creatinine (Male) – mg/dL	1.3 – 2.0	2.1-2.3	>2.3	0.7-1.2
Creatinine (Female) – mg/dL	1.0 – 1.7	1.8 – 2.0	>2.0	0.5 - 0.9
Calcium (hypocalcemia) – mg/dL	8 - <LLN	7.5 – 7.9	<7.5	8.7 - 10.3
Calcium (hypercalcemia) – mg/dL	ULN - 10.8	10.9 – 11.4	>11.4	8.7 - 10.3
CK-U/L	309-1000	1001-1500	>1500	39-308
Albumin (hypoalbuminemia) – g/dL	2.8 – 3.4	2.5 – 2.7	< 2.5	3.5 - 5.2
AST – U/L (Male)	40-97	98-195	>195	<40
AST – U/L (Female)	32-77	78-155	>155	<32
ALT – U/L (Male)	41-100	101-200	>200	<41
ALT – U/L (Female)	33-80	81-160	>160	<33
Alkaline phosphatase – IU/L (Male)	131-260	261-390	>390	40-130
Alkaline phosphatase – IU/L (Female)	106-210	211-315	>315	35-105
Total Bilirubin (serum) – mg/dL	1.3-1.5	1.6-1.9	>1.9	0 - 1.2
Direct Bilirubin – mg/dL	NA	NA	NA	0.0-0.2
Chloride –mEq/L (hypochloremia)	NA	NA	NA	96-108
Chloride –mEq/L (hyperchloremia)	NA	NA	NA	96-108
CO2 –mEq/L (hypo)	NA	NA	NA	20- 30
CO2 –mEq/L (hyper)	NA	NA	NA	20- 30
Total Protein – g/dL	5.5 - 5.9	5.0 - 5.4	<5.0	6.0 - 8.0
Phosphorus- mg/dl (hypo)	2.3-2.4	2.1-2.2	<2.0	2.5 – 4.5
Phosphorus-mg/dl (hyper)	NA	NA	NA	2.5 – 4.5
Total Cholesterol-mg/dl	NA	NA	NA	<201
Triglycerides-mg/dl	NA	NA	NA	<151
HDL – mg/dl	NA	NA	NA	>65 F >55 M

Laboratory Adverse Events*	Mild	Moderate	Severe	ICON Normal Lab Values
	(Grade 1)	(Grade 2)	(Grade 3)	
LDL Direct – mg/dL	NA	NA	NA	<130
Hemoglobin (Male) – g/dL	11.2 - 12.2	10.0 – 11.1	<10.0	12.3-17.3
Hemoglobin (Female) – g/dL	9.8 - 10.8	8.5 - 9.7	<8.5	10.9 - 14.6
WBC Increase – cell/mm ³	10,001– 15,000	15,001 – 20,000	> 20,000	4,000-10,000

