All AE data will be listed for all patients. Both the Investigator's verbatim terms and the MedDRA preferred terms will be listed for each patient. AEs listings will also include start and end date, relationship to study drug, severity, action taken for the AEs and if the AE is serious.

Any SAEs, AEs with outcome of death, or AEs resulting in discontinuation of study or study drug will be listed separately.

AEs recorded as Reactogenicity will be listed by each subject and summarized by dose level and control group similarly as described above. Summaries will be provided for severity and closest relationship.

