## 8. LIST OF TABLES, FIGURES, AND LISTINGS

Table/Figure Number	Table/Figure Name
Section 14.1	Demographic and Subject Characteristics Data Summaries
Table 14.1.1	Summary of Subject Enrollment and Disposition (All Subjects)
Table 14.1.2	Summary of Analysis Populations
Table 14.1.3	Summary of Demographic and Baseline Characteristics (Safety Population)
Section 14.2	Pharmacokinetic and Immunogenicity Data Summaries
Section 14.2.1	Pharmacokinetic Data Summaries
Table 14.2.1.1	Summary of Pharmacokinetic Concentrations (PK Analysis Population) Note: separate for each monoclonal antibody and serotype
Table 14.2.1.2	Summary of Pharmacokinetic Parameters (PK Analysis Population) Note: separate for each monoclonal antibody and serotype
Figure 14.2.1.1	Plot of Mean (SD) Serum Concentration-Time Profile (PK Analysis Population) Note: separate for each monoclonal antibody and serotype
Section 14.2.2	Immunogenicity Data Summaries
Table 14.2.2.1	Summary of Anti-drug Antibody Titers (PK Analysis Population) Note: separate for each monoclonal antibody and serotype
Table 14.2.2.2	Summary of Anti-drug Antibody status (PK Analysis Population) Note: separate for each monoclonal antibody and serotype
Section 14.3	Safety Data Summaries
Section 14.3.1	Displays of Adverse Events
Table 14.3.1.1	Overall Summary of Treatment-Emergent Adverse Events (Safety Population)
Table 14.3.1.2	Summary of Treatment-Emergent Adverse Events by System Organ Class and Preferred Term (Safety Population)
Table 14.3.1.3	Summary of Treatment-Emergent Adverse Events by System Organ Class, Preferred Term, and Maximum Reported Severity Grade (Safety Population)
Table 14.3.1.4	Summary of Treatment-Emergent Adverse Events by System Organ Class, Preferred Term, and Closest Relationship to Study Drug (Safety Population)
Table 14.3.1.5	Overall Summary of Reactogenic Adverse Events (Safety Population)

Table 14.3.1.6      Summary of Reactogenic Adverse Events by System Organ Class, Preferred Term, and Maximum Reported Severity Grade (Safety Population)

Table 14.3.1.7      Summary of Reactogenic Adverse Events by System Organ Class, Preferred Term, and Closest Relationship to Study Drug (Safety Population)

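### The SAP's reactogenicity tables include an other-conditions category and have no onset period, so they may count unrelated illness or vaccine reactions up to Day 120 or Day 180

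*SAP*

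**What the plan says.** SAP section 3.15, after listing the ordinary AE fields, adds: "Reactogenicity (Other conditions, local and systemic reactions) will also be collected". No sentence there says what the first of the three categories covers.

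Protocol Appendix B has a reactogenicity heading with local reactions and systemic reactions under it. The next heading is "All Other conditions", and its single row reads "Illness or clinical AE (as defined according to applicable regulations". The row has severity grades but no limit on cause or time of onset.

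SAP section 7.22.1 sets the content of the reactogenicity outputs: "AEs recorded as Reactogenicity will be listed by each subject and summarized by dose level and control group similarly as described above". It continues: "Summaries will be provided for severity and closest relationship". SAP section 8 lists the results as Table 14.3.1.5 (overall), Table 14.3.1.6 (by system organ class, preferred term and maximum severity) and Table 14.3.1.7 (by system organ class, preferred term and closest relationship).

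On timing, SAP section 3.15 says: "Subjects will be monitored throughout the study for AEs, from the time informed consent is obtained through End of Study (EOS". For Cohorts 1-3, protocol section 4 says: "Last follow up visit scheduled at Day 120". For Cohort 4 the same section puts the last visit at Day 180.

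**The concern.** A reactogenicity table should show how subjects reacted to the injection. For that it needs a rule on which events count and when they must start. Here the event rule includes a category whose only counterpart in the protocol is a residual row for illness, and the time rule is absent.

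Tolerability is part of the primary objective, and these are the only tables dedicated to reactions. If an incidental illness in month three is counted with a sore arm on Day 1, the overall figure no longer measures reaction to the product. Cohort 4 is also followed 60 days longer than the lower doses. Incidental events therefore have more time to accrue at 100 mg, which can look like a dose effect.

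**Working it through.** The plan gives no reactogenicity rate, count or window, so there is no figure to reproduce. The check is mainly textual.

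**1. Do the labels match?** SAP 3.15 names other conditions, local reactions and systemic reactions. Appendix B prints local reactions, systemic reactions and then the all-other heading, in sequence after its reactogenicity heading. SAP 3.15 does not cite Appendix B, so the link is an inference from the labels, but all three correspond.

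**2. What does the residual row hold?** Events not graded elsewhere in Appendix B. Vital signs (including fever), cardiovascular, respiratory and gastrointestinal events and laboratory values have their own rows. A cold without a graded symptom, or an injury, would fall in the residual row.

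**3. Is there an onset limit or a causality filter?** I found none. Outside Appendix B, the protocol mentions reactogenicity only as a data type (section 14.2). Neither schedule of events has a reactogenicity row, and there is no diary or solicitation period. SAP 7.22.1 splits the summaries by relationship but does not exclude unrelated events.

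**4. Is there a foreseeable late source of events?** Protocol sections 4.1.2 (criterion 15) and 5.8 allow an authorised COVID-19 vaccine once Study Day 8 is complete. Section 2.3.1 lists pain, redness, swelling and warmth as risks of an IM injection. A vaccine reaction could therefore fit the local or systemic rows, so removing the other-conditions category alone would not exclude it.

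**5. How large could the effect be?** The documents give no background illness rate. Assume *r* events per person-year, all flagged as reactogenicity. The chance that a subject has at least one by day *d* is

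*p* = 1 − exp(−*r* × *d* / 365).

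| assumed *r* | *d* = 8 | *d* = 120 | *d* = 180 |
|---|---|---|---|
| 0.5 | 1.1% | 15.2% | 21.9% |
| 1 | 2.2% | 28.0% | 38.9% |
| 2 | 4.3% | 48.2% | 62.7% |
| 3 | 6.4% | 62.7% | 77.2% |

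Pooled placebo has 2 subjects per cohort: 6 followed to Day 120 and 2 to Day 180. Mean follow-up is (6 × 120 + 2 × 180) / 8 = 135 days. At *r* = 1, expected incidence in pooled placebo is (6 × 28.0% + 2 × 38.9%) / 8 = 30.7%. The active groups would show 28.0% at 10, 25 and 50 mg and 38.9% at 100 mg, with no drug effect at all.

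**6. How sensitive is this to flagging?** If only a fraction *f* of events is flagged, *r* becomes *f* × *r*. With *r* = 1 and an assumed *f* of 0.1, the result is 1 − exp(−0.1 × 120 / 365) = 3.2% by Day 120 and 1 − exp(−0.1 × 180 / 365) = 4.8% by Day 180. With *f* = 0 it is nil. The figures in step 5 are therefore a ceiling for each assumed rate.

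**The case against.** The strongest reply is that the tables take what is *recorded* as reactogenicity, not every event that fits an Appendix B row. SAP 3.15 treats reactogenicity as an additional item, and protocol section 14.2 names it separately from AEs. The eCRF and the manual of procedures may restrict what a site can flag. This stands: one cannot say that a cold on Day 100 *would* be counted, only that nothing in the two documents prevents it.

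A reader might infer that the reactogenicity tables would largely duplicate the TEAE tables, and that background illness would swamp true reactions. The documents do not support that. The Appendix B row is residual, so cough, nausea, diarrhoea, fever and graded laboratory changes lie outside it and outside the local and systemic rows. Tables 14.3.1.6 and 14.3.1.7 are by preferred term, so injection-site pain or redness keeps its own line, and unrelated illness appears as not related in Table 14.3.1.7. AE listings carry start dates, so late onset can be traced.

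It is also fair to say that unequal follow-up affects every TEAE table, and that Day 8 is the dose-escalation review point rather than a stated reactogenicity limit. Protocol section 2.3.1 names serum sickness-like reactions as a potential risk, so a hard cut at Day 8 could remove a genuine delayed reaction from these tables. Both points stand. The second is why later events should be shown separately rather than dropped.

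What survives is that the SAP names a category that does not belong in a reaction count and states no onset period.

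**Conclusion.** The point holds in limited form. As worded, the SAP allows unrelated illness and late vaccine reactions into Tables 14.3.1.5 to 14.3.1.7 through Day 120 or Day 180. The damage falls mainly on the overall count in Table 14.3.1.5 and on comparing it across dose groups with different follow-up. The severity and relationship tables are less exposed, and the TEAE tables that serve the primary endpoint are not affected.

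The size cannot be computed from the documents. The 28% and 39% are a ceiling that rests on two assumptions found in neither document: 1 background event per person-year, and every such event flagged. They should not be read as the expected result. The textual finding rests on the match of labels between SAP 3.15 and Appendix B, and on the eCRF not narrowing the flag. This should be corrected, but it does not threaten the main safety analysis.

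**What to change.** In SAP 3.15 and 7.22.1, delete the other-conditions category from reactogenicity and base Tables 14.3.1.5 to 14.3.1.7 on the Appendix B local and systemic reaction rows only.

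Within those tables, show events with onset through the Day 8 visit separately from later-onset events. The early part then covers about the same time in every cohort and precedes permitted COVID-19 vaccination. The later part keeps a delayed hypersensitivity reaction in view. All events stay in the TEAE tables.

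Two details need stating. SAP 7.22.1 counts the dosing date as relative day 1, so nominal Day 8 (dosing on Day 0) is relative day 9; the split is best tied to the visit date. Appendix B grades fever under vital signs, so if the sponsor wants it counted as a reaction, that row must be named.

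The cost is SAP wording and one onset-date split. No new data are needed.
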